4. ENDPOINTS

4.1. Efficacy Endpoint

4.1.1. Primary Endpoint

Vaccine efficacy (VE) will be defined as per the applicable regulatory region-specific case definition, as follows:

1. Occurrences of protocol-defined ILI due to laboratory-confirmed influenza (≥ 14 days post-vaccination) caused by any influenza viral type/subtype (RT-PCR).

4.1.2. Secondary Endpoints

- 1. Occurrences of laboratory-confirmed influenza illnesses (according to protocol defined ILI; ≥ 14 days post-vaccination) caused by influenza viral types/subtypes that are matched (and/or antigenically similar) to the strains covered in the vaccine formulation (sequential RT-PCR & serotyping);
- 2. Occurrences of laboratory-confirmed influenza illnesses (according to protocol defined respiratory illness; ≥ 14 days post-vaccination) caused by influenza viral types/subtypes that are matched (and/or antigenically similar) to the strains covered in the vaccine formulation (sequential RT-PCR & serotyping);
- 3. Occurrences of laboratory-confirmed influenza illnesses (according to protocol defined respiratory illness; ≥ 14 days post-vaccination) caused by any influenza viral types/subtypes (matched, mismatched, and un-typed) (sequential RT-PCR);
- 4. Occurrences of protocol-defined ILI ≥ 14 days post-vaccination (confirmed or not by laboratory testing).
- 5. Occurrences of laboratory-confirmed influenza illnesses (according to protocol defined ILI; ≥ 14 days post-vaccination) caused by any influenza viral types/subtypes (matched, mismatched, and un-typed) according to prior exposure to influenza vaccines.

4.1.3. Exploratory Endpoints

- 1. Occurrences of laboratory-confirmed influenza illnesses (according to protocol defined respiratory illness; ≥ 14 days post-vaccination) caused by mismatched influenza viral strains (sequential RT-PCR & serotyping);
- 2. Occurrences of respiratory illnesses \geq 14 days post-vaccination (confirmed or not by laboratory testing).
- 3. The slope estimate of the weighted Schoenfeld residuals against event time based on the Cox proportional hazard model for the primary endpoint, that is, protocol-defined ILI caused by any influenza viral type/subtype.

4.2. Safety Endpoints

4.2.1. Secondary Endpoints

- 1. Percentage, intensity, and relationship to vaccination of immediate complaints (15 minutes post-vaccination);
- 2. Percentage, intensity, and relationship to vaccination of solicited local and systemic signs and symptoms (for seven days following study vaccine administration);
- 3. Percentage, intensity, and relationship of TEAEs for 21 days following study vaccine administration;
- 4. Occurrences of deaths, SAEs, AEs leading to withdrawal, and NOCDs up to the end of the surveillance period.

4.2.2. Exploratory Endpoint

1. Information on respiratory illness outcome, occurrences of pneumonia, new onset or exacerbations of cardio-respiratory conditions, and health care utilization during the entire trial follow up period.

4.3. Immunogenicity Endpoints

4.3.1. Secondary Endpoints

HI antibody response induced against the homologous and heterologous influenza strains on Days 0 and 21 in a subset of 420 subjects (210 from each of the two treatment groups). HI antibody titers will be analyzed as follows:

- 1. Geometric mean titer (GMT) of HI antibody on Days 0 and 21;
- 2. Seroconversion (SC) rate: the proportion of subjects in a given treatment group with either a ≥ 4-fold increase in reciprocal HI titers between Day 0 and Day 21 or a rise of undetectable HI titer (i.e. < 10) pre-vaccination (Day 0) to an HI titer of ≥ 40 on Day 21;
- 3. Seroprotection (SP) rate: the proportion of subjects in a given treatment group attaining a reciprocal HI titer of \geq 40 on Day 21 (the percentage of vaccine recipients with a serum HI titer of at least 1:40 following vaccination);
- 4. Geometric mean fold rise (GMFR): the geometric mean of the ratio of GMTs (Day 21/Day 0).

MN antibody response induced by the Quadrivalent VLP Influenza Vaccine against the homologous influenza strains on Days 0 and 21, in the subset of subjects, will be analyzed as follows:

- 1. GMT of MN antibody on Days 0 and 21;
- 2. SC rate on Day 21: the proportion of subjects in a given treatment group with either $a \ge 4$ -fold increase in reciprocal MN titers between Day 0 and Day 21 or a rise of

undetectable MN titer (i.e. 7.1) pre-vaccination (Day 0) to an MN titer of \geq 28.3 at Day 21 post-vaccination

3. GMFR: the geometric mean of the ratio of GMT (Day 21/Day 0).

SRH antibody response induced by the Quadrivalent VLP Influenza Vaccine against the homologous strains on Days 0 and 21 in a subset of subjects, will be analyzed as follows:

- 1. Geometric mean area (GMA) of SRH antibody on Days 0 and 21;
- 2. SC rate: proportion of subjects in a given treatment group showing at least 50 % increase in GMA between Days 0 and 21;
- 3. SP rate: the proportion of subjects in a given treatment group attaining an area ≥ 25 mm² following vaccination (Day 21);
- 4. GMFR: the geometric mean of the ratio of GMA (Day 21/Day 0).

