12.6.1 Analysis of Secondary Endpoints

The secondary immunogenicity endpoints are defined in Section 10.4.2.1.

The following analyses for the HI assay (homologous strains) will be performed on the immunogenicity PP:

- GMT (Day 21): The point estimates and the corresponding two sided 95 % CI by treatment group and strain will be calculated as the antilog of the mean and 95 % CI of log transformed titer values;
- SC rate (Day 0 and Day 21): The point estimates and the corresponding two-sided 95 % CI for subjects achieving SC by treatment group and strain will be calculated to determine whether the lower bound of the CI will meet or exceed 30 %;
- SP rate (Day 21): The point estimates and the corresponding two-sided 95 % CI for subjects achieving SP by treatment group and strain will be calculated to determine whether the lower bound of the CI will meet or exceed 60 %.

The analyses for the MN and SRH assays (homologous strains) will be performed on the immunogenicity PP. The GMT, GMFR, and SC rate of the MN antibody assay and the GMA, GMFR, SC rate, and SP rate for the SRH antibody assay will be compared between the treatment groups using descriptive statistics and 95 % CI. For SC rate and SP rate, Fisher's exact tests or chi square tests will be used. GMT and GMFR for MN and GMA and GMFR for SRH will be compared using appropriate analysis of variance models.

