6.3.5. Immunogenicity

Values below the HI antibody responses below the lower limit of quantification (Below limit of Quantification (BLQ)<10, recorded as "< 10") will be attributed a value of 5. All BLQ responses for the SRH antibody will be attributed a value of 2 mm².

For HI assay:

SC rate is defined as the proportion of subjects in a given treatment group with either $a \ge 4$ -fold increase in reciprocal HI titers between Day 0 and Day 21 or a rise of undetectable HI titer (i.e. < 10) pre-vaccination (Day 0) to an HI titer of ≥ 40 on Day 21.

SP rate is defined as the proportion of subjects in a given treatment group attaining a reciprocal HI titer of ≥ 40 on Day 21 (the percentage of vaccine recipients with a serum HI titer of at least 1:40 following vaccination).

For MN assay:

SC rate is defined as the proportion of subjects in a given treatment group with either $a \ge 4$ -fold increase in reciprocal MN titers between Day 0 and Day 21 or a rise of undetectable MN titer (i.e. 7.1) pre-vaccination (Day 0) to an MN titer of ≥ 28.3 at Day 21 post-vaccination.

For SRH assay:

SC rate is defined as the proportion of subjects in a given treatment group showing at least 50 % increase in GMA between Days 0 and 21.

SP rate is defined as the proportion of subjects in a given treatment group attaining an area $\geq 25 \text{ mm}^2$ following vaccination (Day 21).

GMT calculation:

The GMT calculations are performed by taking the anti-log of the mean of the log titer transformations. The back-transformation for mean GMT will be calculated with two-sided, 95% confidence limits, based on the Analysis of Variance (ANOVA) model.

GMFR calculation:

The GMFR will be derived by using Analysis of Covariance (ANCOVA) to model the difference in the log of the titer values between Day 21 and Day 0, with treatment group as main effect and baseline titer as covariate. The GMFR will be compared between the treatment groups. The comparisons between the treatment groups will be performed using two-sided, 95% confidence, based on the least-squares mean differences from the ANCOVA model.

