9.2. Analysis of Secondary Endpoints

The secondary immunogenicity endpoints are defined in Section 4.3.1.

HI antibody titers will be analyzed and evaluated as follows:

- GMTs of HI antibody: The point estimates and the corresponding two sided 95 % CI by treatment group and strain will be calculated as the antilog of the mean and 95 % CI of log transformed titer values on Days 0 and 21;
- SC rate: The point estimates and the corresponding two-sided 95 % CI for subjects achieving SC by treatment group and strain will be calculated and reported;
- SP rate: The point estimates and the corresponding two-sided 95 % CI for subjects achieving SP by treatment group and strain will be calculated and reported.
- GMFR: the geometric mean of the ratio of GMTs (Day 21/Day 0).

MN antibody response against the homologous influenza strains on Days 0 and 21 will be analyzed as follows:

- GMTs of MN antibody on Days 0 and 21(as defined above for HI);
- SC rate: the proportion of subjects in a given treatment group with either a ≥ 4-fold increase in reciprocal MN titers between Day 0 and Day 21 or a rise of undetectable MN titer (i.e. 7.1) pre-vaccination (Day 0) to an MN titer of ≥ 28.3 at Day 21 post-vaccination.
- GMFR: the geometric mean of the ratio of GMTs (Day 21/Day 0).

SRH antibody response against the homologous influenza strains will be analyzed as follows:

- GMAs of SRH antibody on Days 0 and 21;
- SC rate: proportion of subjects in a given treatment group showing at least 50% increase in GMA between Days 0 and 21;
- SP rate: the proportion of subjects in a given treatment group attaining an area ≥ 25 mm² following vaccination (Day 21);
- GMFR: the geometric mean of the ratio of GMAs (Day 21/Day 0).

The GMFR will be derived by using ANCOVA to model the difference in the log of the titer values between Day 21 and Day 0, with treatment group as main effect and baseline titer as covariate

The GMTs, GMFRs, SP and SC rates of the HI antibody assay, the GMTs, GMFRs and SC rates of and the MN antibody assay, and the GMAs, GMFRs, SC rates, and SP rates for the SRH antibody assay will be compared between the treatment groups using descriptive statistics and 95% CI.

For SC rate and SP rate, Fisher's exact tests will be used. GMT for HI, MN and GMA for SRH will be compared between treatment groups using the ANOVA model. GMFR for HI, MN and SRH will be compared using the ANCOVA model.

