9.2.2.2. Exact 95% CIs

The exact 95% CIs (Clopper-Pearson method) will be used for proportion of SC and SP subjects within a group.

SAS® Code for SC and SP (Exact 95% CIs):

```
PROC FREQ data=<Data>;
    BY ANTIGEN trtpn;
    TABLE SC/out=CNT binomial; *SC or SP
    EXACT binomial;
    ODS OUTPUT binomialprop=bin (where=(name1 in ('XL_BIN', 'XU_BIN')));
run;
```

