12. CHANGES FROM ANALYSIS PLANNED IN PROTOCOL

- 1). According to the scientific advices of European Medicines Agency (EMA), a new secondary efficacy endpoint is added:
 - Occurrences of laboratory-confirmed influenza illnesses (according to protocol defined ILI; ≥ 14 days post-vaccination) caused by any influenza viral types/subtypes (matched, mismatched, and un-typed) according to prior exposure to influenza vaccines.

The occurrence and vaccine efficacy (95% CI) for subjects with and without influenza vaccination history will be summarized.

- 2). A new exploratory efficacy endpoint is added:
 - To evaluate whether or not vaccine efficacy (VE) is maintained (no waning) through time after vaccination for the primary efficacy endpoint, that is, protocol-defined ILI caused by any influenza viral type/subtype.

The relevant analysis is described in Section 8.4.

3). Heterologous strains for the exploratory CMI data will not be analyzed due to the reason below:

As it was already demonstrated in previous clinical trials that the Quadrivalent VLP Influenza Vaccine elicited cross-reactive CD4 T cell response, it was decided to wait so see if the 2018-2019 season would be a match or a mismatch season. In case of a mismatch season, Medicago will therefore has the possibility to test the CMI response generated by the Quadrivalent VLP Influenza Vaccine against the strain(s) that were actually circulating during the season.

4). There is a discrepancy between the protocol and the SAP regarding the seroconversion calculations for MN titers. The definition used in the SAP (cut-off at 7.1) is the one prevailing over the protocol definition (in which it is said that the same approach as for HI titers will be used).

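### HI seroconversion: with titres below 10 set to 5 and no baseline limit on the four-fold rule, a change from <10 to 20 counts, and the ≥40 condition for undetectable baselines never changes a classification

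*SAP*

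**What the plan says.** **Definition.** SAP 4.3.1 defines the HI seroconversion rate by two routes joined by either/or. The first is a rise of at least four-fold. The second covers subjects who are undetectable at Day 0. The wording runs "increase in reciprocal HI titers between Day 0 and Day 21 or a rise of undetectable HI titer (i.e. < 10" and then "pre-vaccination (Day 0) to an HI titer of ≥ 40 on Day 21". SAP 6.3.5 and Protocol 10.4.2.1 carry the same rule. None of the three limits the four-fold route to detectable baselines.

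**Substitution.** SAP 6.3.5 opens by stating that HI results recorded as below 10 "will be attributed a value of 5". The seroconversion definition follows in the same section. Nothing restricts the value 5 to the GMT or GMFR calculations.

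**Analysis.** SAP 9.2 says of the HI rate only that the estimate and CI "for subjects achieving SC by treatment group and strain will be calculated and reported", and it compares arms with Fisher's exact test. The sample code in SAP 9.2.2.2 starts from a seroconversion flag that already exists ("TABLE SC/out=CNT binomial; *SC or SP") and does not show how it is derived. Protocol 12.6.1 goes further: the HI rate and its CI are "calculated to determine whether the lower bound of the CI will meet or exceed 30" per cent.

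**Changes list.** SAP section 12 deals with seroconversion for MN only ("There is a discrepancy between the protocol and the SAP regarding the seroconversion calculations for MN titers").

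**The concern.** The separate ≥40 requirement for undetectable baselines looks intended to stop a small rise from an unmeasurable titre being counted as a response. Once <10 becomes 5 and the four-fold route is open to every baseline, that protection disappears: a subject going from <10 to 20 qualifies by the first route while failing the condition written for exactly that kind of subject.

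Two consequences follow. First, two programmers could derive different HI seroconversion rates and each claim to follow the text. One would apply 5 throughout; the other would let ≥40 govern undetectable baselines. Second, the discrepancy has a direction: the as-written rule can only keep or raise each arm's rate, and Protocol 12.6.1 compares the lower confidence bound of that rate with a fixed 30%. Protocol 1.3.2.1 reports that in the earlier study in subjects aged 65 and older the 30 µg/strain dose met the seroconversion criterion against H3N2 only, so upward movement in this rate is worth ruling out.

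**Working it through.** The plan states no figure for this point, so there is none to reproduce. The check concerns the logic of the rule, followed by an illustration of size.

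**Inputs from the documents**
- Substituted value for HI <10: 5 (SAP 6.3.5).
- Route 1: Day 21 / Day 0 ≥ 4. Route 2: Day 0 < 10 and Day 21 ≥ 40 (SAP 4.3.1 and 6.3.5; Protocol 10.4.2.1).
- MN counterpart: "undetectable MN titer (i.e. 7.1) pre-vaccination (Day 0) to an MN titer of ≥ 28.3 at Day 21 post-vaccination" (SAP 9.2).
- Subset: 210 per arm (SAP 4.3.1). CI: Clopper-Pearson (SAP 9.2.2.2).

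**Step 1: ratios**
- <10 to 20: 20/5 = 4, so route 1 is met.
- <10 to 40, the smallest change that meets route 2: 40/5 = 8, so route 1 is already met.
- MN: 28.3/7.1 = 3.99. The MN threshold is a four-fold step from its undetectable value, and with these rounded figures route 2 admits a change that a strict ≥4 test would miss. The HI threshold is an eight-fold step from 5, so there the two routes disagree about <10 to 20.

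**Step 2: enumeration.** Take all 8 × 8 = 64 Day 0 / Day 21 pairs on the two-fold scale 5, 10, 20, …, 640 (an assumed dilution scale).

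| Comparison | Pairs classified differently |
|---|---|
| As written vs. four-fold route alone | 0 |
| As written vs. four-fold only if Day 0 ≥10, and ≥40 if Day 0 <10 | 1 (5 to 20) |

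On a half-step grid the second comparison also picks up 5 to 28.3; the first still shows none.

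**Step 3: size within an arm**

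Rise in rate = P(Day 0 <10) × P(20 ≤ Day 21 <40 given Day 0 <10)

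The documents give neither probability. Assuming 10–50% for the first and 10–30% for the second:
- Low: 0.10 × 0.10 = 1.0 point; 0.010 × 210 = 2.1 subjects.
- Middle: 0.30 × 0.20 = 6.0 points; 0.060 × 210 = 12.6 subjects.
- High: 0.50 × 0.30 = 15.0 points; 0.150 × 210 = 31.5 subjects.

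A simulation ties the two probabilities to the baseline GMT. All of its settings are assumed: log2 SD 1.7 at baseline and 1.5 for the rise, GMFR 2–3, two titre-rounding conventions, one million subjects.

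| Baseline GMT | Rise in rate (points) |
|---|---|
| 10 | 5.7–9.0 |
| 20 | 3.2–5.6 |
| 30 | 2.0–3.8 |
| 60 | 0.7–1.4 |
| 100 | 0.3–0.6 |

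**Step 4: the 30% bound.** With n = 210 the lower Clopper-Pearson bound is 29.7% at 76 responders and 30.1% at 77 (36.7%), so 77 are needed. As illustration only: 63/210 (30.0%) has a lower bound of 23.9%. If a further 5% of subjects are counted, 74/210 has 28.8%; if 10%, 84/210 has 33.3%. Whether any real result lies near 77 is unknown.

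**Step 5: between arms.** The shift in the difference is P(Day 0 <10) × (difference between arms in the second probability). It is 0 if that probability is equal in both arms. If it differs by 10 points, the shift is 0.10 × 10 = 1 to 0.50 × 10 = 5 points.

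**The case against.** The strongest counter-argument is that the SAP never says 5 is the denominator of the fold-rise test. The log-scale GMT and GMFR need a numeric substitute in any case, and the second route is worded by detection status. On that view the route naming undetectable baselines governs them, both routes do some work, and the proposed wording only restates what was meant. The MN rule can be read in support: 40 is four times the HI cut-off of 10, just as 28.3 is about four times 7.1. This is probably the intended meaning, but the text does not say it. Either/or, together with an unrestricted substitution in the same section, gives the other result, and neither SAP 9.2 nor the sample code settles the matter.

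Three further points stand in whole or part:
- SAP section 12 lists departures from the protocol. The HI wording is the same in both documents, so its absence there is no evidence of oversight. It means only that section 12 does not resolve the question.
- The size rests entirely on assumptions. The 15-point upper end exceeds every simulated scenario (maximum 9.0) and should be read as an outer limit.
- This is a secondary endpoint in 420 of about 12,120 subjects, with no multiplicity adjustment, and the SAP itself reports the rate without applying the 30% test.

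Program quality control (SAP section 15) checks logic, but it cannot choose between two readings that the specification leaves open.

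**Conclusion.** The concern holds. As written, <10 to 20 counts as HI seroconversion and the ≥40 condition never alters a classification. That redundancy does not depend on the exact substitute: any value up to 10 gives at least 40/10 = 4. The <10 to 20 result does depend on the value 5.

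Against the rule's own ≥40 condition, the rate in each arm can only stay equal or rise. The amount could be a fraction of a point if few subjects start below 10, or several points if many do; the documents do not allow it to be narrowed. No crossing of the 30% bound is claimed. The rule applies to both arms, so between-arm bias would need the arms to differ in their share of <10 to 20 subjects, and nothing in the documents suggests they do. Primary efficacy is untouched. This should be corrected as a matter of specification; it does not threaten the trial's main conclusion.

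**What to change.** Before database lock, replace the HI rule in SAP 4.3.1 and 6.3.5 with: *HI seroconversion: Day 0 titre ≥10 and a ≥4-fold rise, or Day 0 titre <10 and Day 21 titre ≥40.* Add an entry to SAP section 12, beside the MN item, stating that this clarifies the rule in Protocol 10.4.2.1, so that the unchanged protocol wording does not become a new discrepancy.

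The cost is one sentence in two sections, one line in section 12 and one line of code. The only downside is that the reported HI seroconversion rates may be slightly lower than under the as-written rule.

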4.3.2. Exploratory Endpoint

CMI response induced by the Quadrivalent VLP Influenza Vaccine against homologous strains on Day 21 (subset of 420 subjects), as measured by the number of CD4+ T cells expressing each of three functional markers: interferon gamma (IFN- γ), interleukin-2 (IL-2), and tumor necrosis factor alpha (TNF- α), as well the number of cells producing at least one of these cytokines and the number of cells producing two or more of these cytokines.

5. ANALYSIS SETS

5.1. Safety Analysis Set

The safety analysis set (SAS) is defined as all subjects who received either the Quadrivalent VLP Influenza Vaccine or the active comparators. All safety analysis will be performed using the SAS, according to the treatment the subjects actually received.

5.2. Full Analysis Set

The full analysis set (FAS) will consist of the subset of subjects in the SAS who were successfully contacted at least once during the surveillance period. Subjects who received the wrong treatment will be analyzed as randomized.

5.3. Per Protocol Set

The per protocol (PP) set will consist of the subjects who participated in the study until at least the end of the peak period (approximately the end of February for Europe and North America) or for at least five months or until the end of the surveillance period (other countries); had no major protocol deviations related to subject eligibility, the ability to develop a valid immune response, prohibited medication use, or the efficacy analyses; and who received the VLP vaccine or the active comparator. Major protocol deviations will be identified and documented during a blinded data review prior to database lock and confirmed at the time of database lock. The PP set will be the primary analysis population for the efficacy and immunogenicity endpoints. Subjects who received the wrong treatment, but for whom the treatment received can be unequivocally confirmed, will be analyzed as treated, provided they have no other deviations that compromise their data.

The analyses of all efficacy endpoints will be performed using the efficacy PP population and the FAS population.

Note: Protocol deviations and the definition of the peak influenza period will be reviewed and documented during a blinded data review prior to database lock and confirmed at the time of database lock. Since peak influenza period in each region can vary from year to year, the exact period for individual regions will be defined at the end of the season, based on reported positive influenza tests (regional surveillance reporting). The handling of missing data and whether the potential impact of any protocol deviations require the exclusion of a subject from analyses will also be considered during the blinded data review.

